6.7.1.2. Adverse Reaction (AR)

An adverse reaction (AR) is an untoward and unintended response to the treatment administered or the procedure performed. All AEs judged by either the reporting investigator or the sponsor as having reasonable causal relationship to Grazax®/Grazax® Placebo or the different procedures performed qualify as adverse reactions. The expression reasonable causal relationship means to convey in general that there is evidence or argument to suggest a causal relationship.

There are a number of procedures throughout the study which are associated with expected symptoms. These include the following:

- AIT involves taking a daily tablet under the tongue. This is frequently associated with oral itching and mild swelling. These symptoms may last from minutes to hours or longer in some cases. As long as these symptoms are not bothersome (i.e. interfere with usual daily activities or sleep) they will not be reported as ARs.
- Non-invasive nasal secretion collection techniques using nasal sponges are not expected to cause any significant adverse events. Whilst the sponges are in place there is a degree of discomfort and a sensation of nasal blockage felt by the participant. Rarely there is mild nasal bleeding. As long as the reactions are not bothersome (interfere with sleep or with daily activities) it will not be reported as ARs.
- Intradermal skin tests at the planned concentrations are entirely safe, without risk of systemic allergic reactions in grass pollen allergic individuals. As long as the reactions are not bothersome (interfere with sleep or with daily activities) they will not be reported as ARs.
- Nasal biopsy is completely painless whereas following the procedure there may be slight bleeding and/or discomfort that responds to paracetamol. Bleeding responds to gentle local pressure applied *bilaterally to the outside* of the nose

by the volunteer. Discomfort may last up to 24 hours, very rarely for several days, is mild and responds to paracetamol. As long as bleeding responds to finger pressure, mild discomfort responds to paracetamol, and consultation with a study physician is not required, they will not be reported as ARs. Should further measures be required, participants will have 24 hour access to advice from members of the study team.

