6.5.9 Intradermal skin tests

Intradermal skin tests are performed by injecting 0.02ml of allergen diluted in albumin-based diluent into the skin of the outer surface of the forearms. 1 BU (0.02ml of 50

BU/ml) will be injected into the right and the left forearm. A negative control injection of 0.02ml of normal saline will be injected on the outer surface of the wrist on the right.

Skin responses are defined as follows:

Response	Skin Allergen Challenge
Early Phase Response (EPR)	Measured 15 Minutes after Allergen Challenge \pm 5 min
Late Phase Response (LPR)	Measured 8 Hours after Allergen Challenge \pm 1 hour

In pollen sensitized individuals, allergen skin injection provokes a local wheal and flare skin response, peaking at about 15 minutes. This is recorded in comparison with the negative control (saline) injection. In sensitized, allergic individuals, following resolution of the early wheal and flare response, there is a gradual onset mild swelling and redness over a larger area around the site of the injection – the LPR. This response is measured at 8 hours after injection using a pencil-friction technique to map out the extent of skin swelling. Volunteers may experience mild to moderate itchiness or local discomfort at the sites of intradermal injections and skin pricks with allergen. The symptoms are not bothersome and treatment with oral antihistamines is always available and is effective although almost never required. Systemic reactions including anaphylaxis after skin tests with standardized aeroallergen extracts are a theoretical risk but exceedingly rare. However, a physician is always present and drugs and equipment for treatment of anaphylactic reactions available.

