6.7.2 Grading of adverse events/adverse reactions

The study site will grade the severity of AEs/ARs for the study medication according to the following criteria:

- All local reactions not associated with systemic signs or symptoms will be graded according to Table 6.
- All systemic reactions to AIT will be graded according to the WAO SCIT Reaction Grading System³⁵. The following modification will apply for AIT: Under Grade 1 (Symptoms/signs of 1 organ system present), “throat clearing (itchy throat)” is not considered a systemic reaction.

Table 6: Sublingual immunotherapy (local reactions) Grade Description²⁹

Symptom/sign (see Table I)	Grade 1: Mild	Grade 2: Moderate	Grade 3: Severe	Unknown severity
Pruritus/swelling of mouth, tongue, or lip; throat irritation, nausea, abdominal pain, vomiting, diarrhea, heartburn, or uvular edema	
 Not troublesome AND No symptomatic treatment required AND No discontinuation of SLIT because of local side effects 	
 Troublesome OR Requires symptomatic treatment AND No discontinuation of SLIT because of local side effects 	
 Grade 2 AND SLIT discontinued because of local side effects 	Treatment is discontinued, but there is no subjective, objective, or both description of severity from the patient/physician.

Each local AE can be early (<30 minutes) or delayed.

The study site will grade the severity of AEs/ARs for the following selected study procedures according to the following criteria:

- All local reactions to nasal biopsy will be recorded according to Table 7.
- All local reactions to allergen skin testing that are to be reported as AEs and are not associated with systemic signs or symptoms will be graded according to Table 8.
- Although very unlikely, systemic reactions related to either AIT tablet treatment, nasal challenge or intradermal or skin prick test procedures will be graded according to the WAO SCIT Systemic Reaction Grading System³⁵.

Table 7: Nasal biopsy procedure (local reactions)

Grade Description

1 Bleeding that does not respond to finger pressure, pain that does not respond to paracetamol, or symptoms which require a telephone consultation with a study physician.

2 Bleeding or pain that requires a visit to the doctor for treatment.

3 Bleeding or pain that requires hospitalization.

Table 8: Intradermal and skin prick test procedure (local reactions)

Grade Description

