1 Bothersome (interfering with usual daily activities or sleep).

2 Bothersome (requiring medication).

3 Bothersome (requiring a visit to the study physician/emergency room for treatment).

The study site will grade the severity of AEs/ARs experienced by study participants not covered by Tables 5 through 7 or mentioned in the WAO criteria³⁵ according to the criteria set forth in the National Cancer Institute's *Common Terminology Criteria for Adverse Events, Version 4.0* (published May 28, 2009 and updated June 14, 2010). This document is found at this website:

http://evs.nci.nih.gov/ftp1/CTCAE/CTCAE_4.03_2010-06-14_QuickReference_5x7.pdf.

This document (referred to herein as the “NCI-CTCAE manual”) provides a common language to describe levels of severity, to analyse and interpret data, and to articulate the clinical significance of all AEs. AEs will be graded on a scale from 1 to 5 according to the following standards in the NCI-CTCAE manual:

- Grade 1 = mild adverse event.
- Grade 2 = moderate adverse event.
- Grade 3 = severe and undesirable adverse event.
- Grade 4 = life-threatening or disabling adverse event.
- Grade 5 = death.

For additional information and a printable version of the NCI-CTCAE manual, go to http://ctep.cancer.gov/protocolDevelopment/electronic_applications/ctc.htm#ctc_40

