6.7.6.4 Reporting

All AEs and ARs as defined in section 6.7.1.1 to 6.7.1.6 will be reported. Depending on the nature of the event the reporting procedures below will be followed. Any questions concerning AEs reporting will be directed to the study coordinator in the first instance. Again the recommended flow chart in JRCO/SOP/001 will be used to further assess AEs³¹.

Non serious AR/AEs

All AR and AEs, whether expected or not, will be recorded on the patient notes and on the relevant CRF and will be collected in the study coordination centre.

SARs/SAEs

If the AR or AEs is considered to be serious (SAEs or SARs) the SAE form will be filled out appropriately stating the nature of event, date of onset, severity, corrective therapies given, outcome and causality (i.e. unrelated, unlikely, possible, probably, definitely). The responsible investigator will sign the causality of the event. Additional information will be filled in within 5 days if the reaction has not resolved at the time of reporting. The CI will send all SAE reports to the Joint Research Compliance Office, Imperial College AHSC as soon as possible after becoming aware of the event. Notification will be performed to the MHRA, REC and the Sponsor of all SAEs as soon as possible. SAEs will be included in the annual safety report.

SUSARs

In the case of SUSARs, we will: Complete the SAE case report form signed and dated together with relevant treatment forms and anonymised copies of all relevant investigations and we will notify expedited the MHRA, REC and the Sponsor of all SUSARs according to the following timelines:

- as soon as possible but not later than 7 calendar days in case of fatal and life threatening SUSARs
- as soon as possible but not later than 15 calendar days in case of non-fatal and non-life threatening SUSARs.

Notification will further take place through the e-SUSAR account further described in the SPOP JRCO/SOP/001³¹. All investigators will be informed of all SUSARs occurring throughout the study. The CI will include all SSARs and SUSARs in the annual safety report.

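### The protocol's exemption for tablet mouth reactions ignores treatment and stopping, so a reaction its own Table 6 grades 2 or 3 may go unrecorded, in conflict with the SAP

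*Protocol*

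**What the plan says.** **Tablet.** Protocol 6.7.1.2 lists procedures with expected symptoms. Of the daily tablet it says "This is frequently associated with oral itching and mild swelling", and then: "As long as these symptoms are not bothersome (i.e. interfere with usual daily activities or sleep) they will not be reported as ARs".

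**Intradermal tests.** The same list calls these tests "without risk of systemic allergic reactions in grass pollen allergic individuals" and adds: "As long as the reactions are not bothersome (interfere with sleep or with daily activities) they will not be reported as ARs".

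**Collection.** Protocol 6.7.6 puts non-serious events on the case report form only if 6.7.1.1 and 6.7.1.2 do not exclude them. Protocol 6.7.6.2 limits collection in the same way.

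**Grading.** In Table 6 of 6.7.2, a local tablet reaction is Grade 1 only if it is not troublesome, is untreated and does not lead to stopping. Grade 2 is reached if it is troublesome or "Requires symptomatic treatment". Grade 3 is Grade 2 with the tablet stopped because of it. Table 8 grades local skin-test reactions, and its Grade 2 is "Bothersome (requiring medication".

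**Rules that point the other way.** Protocol 6.7.6.3 has the investigator record adverse events whatever their severity. Protocol 6.7.6.4 says: "All AR and AEs, whether expected or not, will be recorded on the patient notes and on the relevant CRF". SAP 8.2 makes a treatment side effect an adverse event once it exceeds Grade 1, and tabulates events that led to stopping study drug.

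**The concern.** The exemption and the grading table use different tests. The exemption asks only whether activities or sleep were disturbed. Table 6 also asks whether the reaction was treated and whether the tablet was stopped. A participant who takes an antihistamine for an itchy mouth but works and sleeps normally passes the first test and fails the second. The case is foreseeable, since Protocol 6.4.4 says antihistamine treatment should be considered for significant local reactions. The biopsy item in the same list of exemptions does ask about response to treatment and need for consultation, so the tablet and skin-test items are the ones out of line.

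Secondary objective 3 in Protocol 5.2 is to document whether local and systemic side effects of the tablet occur and how severe they are. If staff apply the exclusion as written, the adverse event tables in SAP 8.2, including the row for stopping study drug, can lack events that the SAP intends to count.

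**Working it through.** The plan gives no figure to reproduce. The check sets each type of reaction, assumed not to disturb activities or sleep, against each rule.

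| Reaction | Exemption (6.7.1.2, applied by 6.7.6 and 6.7.6.2) | Grade (6.7.2) | SAP 8.2 | Result |
|---|---|---|---|---|
| Mouth itching or mild swelling, not troublesome, untreated, tablet continued | Excluded | Table 6 Grade 1 | Not an adverse event | Consistent |
| Same, but treated | Excluded | Table 6 Grade 2 | Adverse event | Conflict |
| Same, treated and tablet stopped for it | Excluded | Table 6 Grade 3 | Adverse event, and in the row for stopping study drug | Conflict |
| Other Table 6 symptoms, such as vomiting or uvular oedema | Not covered | Table 6 | By grade | No exemption |
| Systemic reaction to the tablet | Not covered | WAO systemic scale | By grade | No exemption |
| Local skin-test reaction needing medication or a visit | Excluded by the definition in 6.7.1.2 | Table 8 Grade 2 or 3, labelled bothersome | Threshold is for treatment side effects, so not decisive | Ambiguous |
| Systemic skin-test reaction | Item does not say local only | WAO systemic scale | As above | Ambiguous |

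**Tablet rows.** These rest on the treatment route to Grade 2. *Troublesome* is not defined. If it means more than disturbed activities or sleep, some untreated reactions fall into the same conflict.

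**Skin-test rows.** In 6.7.1.2 *bothersome* means disturbed activities or sleep. In Table 8 that is only Grade 1, while medication and a visit are Grades 2 and 3 of the same word. Table 8 cannot settle the matter, because 6.7.2 applies it only to local reactions already due to be reported. On systemic risk, 6.7.1.2 denies it, while 6.5.9 says "Systemic reactions including anaphylaxis after skin tests with standardized aeroallergen extracts are a theoretical risk" (adding that such reactions are very rare) and 6.7.2 provides for grading them.

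**Could other data recover the event?** The diary in Protocol Appendix 9 asks about itching, swelling, other symptoms, whether they were bothersome, and the reason for a missed tablet. It has no field for symptomatic treatment, which is what lifts a non-troublesome reaction to Grade 2. The schedule in SAP 10.2.1 records concomitant medication at the visits, but no text links an entry to a mouth reaction.

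**Size.** Protocol 6.4.1 cites local reactions in 50% to 60% of those treated. With at least 44 randomised and at most 50 enrolled, 1:1, the active arm has 22 to 25 participants. The expected number with any local reaction is 0.50 × 22 = 11 to 0.60 × 25 = 15. This is only the pool from which affected cases come. The share treated without disturbed activities or sleep is not given, and 6.4.1 says these reactions generally need no treatment.

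**The case against.** The strongest reply is that the data are not lost. SAP 8.2 already makes Grade 2 and 3 tablet reactions adverse events, and Protocol 6.7.6.3 and 6.7.6.4 point to recording everything. SAP 7.3.1 item 3 also grades local tablet symptoms daily from the diary, whatever their reporting status.

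Much of this stands. A reader might infer that these reactions certainly go unreported, and the documents do not support that. They contain competing rules. The reply does not remove the conflict, though. Sections 6.7.6 and 6.7.6.2 name the exclusions, while 6.7.6.3 is general and 6.7.6.4 refers back to the definitions that contain them. The SAP can count only what has been recorded. The diary grading is an exploratory endpoint, separate from the adverse event tables, and lacks the treatment item.

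Other stronger readings also fail:

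- **Systemic reactions are exempt.** For the tablet they are not, since the exemption covers only mouth itching and mild swelling. For skin tests, 6.7.2 requires systemic grading with no bothersome test, so the unqualified wording is a drafting ambiguity.
- **Treated skin-test reactions are clearly exempt.** Table 8 calls them bothersome, and 6.5.9 says treatment is almost never needed.
- **The loss falls almost wholly on the active arm.** No placebo rate of mouth reactions is given, and both arms have skin tests.
- **The row for stopping study drug could be emptied.** The 5% withdrawal in 6.4.1 is not attributed to mouth reactions, and placebo was 3%. The 2-point excess is 0.02 × 22 = 0.44 to 0.02 × 25 = 0.5 participants, for any cause.

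**Conclusion.** The concern holds as a conflict between rules and should be corrected. For tablet-related mouth itching and mild swelling, the protocol's collection rule excludes treated reactions, and treated reactions that led to stopping, when activities and sleep were undisturbed. Table 6 grades these 2 or 3, SAP 8.2 counts them, and Protocol 6.7.6.3 and 6.7.6.4 point to recording them. They may go unrecorded, depending on which rule staff follow.

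The skin-test item is a lesser problem of wording: two meanings of one word, no limit to local reactions, and a statement on systemic risk that conflicts with 6.5.9 and 6.7.2.

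The number affected cannot be estimated, and no direction or size of bias between the arms can be shown. The conclusion assumes that the WAO grade in SAP 8.2 is the Table 6 grade for local reactions, which the SAP does not say outright.

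**What to change.** In Protocol 6.7.1.2:

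1. Exempt a tablet mouth reaction only if it meets all three Table 6 Grade 1 conditions. This matches the SAP 8.2 threshold. State that disturbed activities or sleep counts as troublesome, so that nothing now reportable drops out.
2. Exempt a skin-test reaction only if it is local and below every Table 8 grade: no disturbance of activities or sleep, no medication and no visit.
3. State that systemic reactions are never exempt, in line with 6.7.2.
4. Reconcile the denial of systemic risk with 6.5.9.

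Sections 6.7.6 and 6.7.6.2 then inherit the revised exclusion. If recording has begun under the present wording, the report should say which rule was applied.

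The cost is wording, a few more adverse reaction records, and a slightly higher reported adverse reaction rate.

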6.7.1.3. Unexpected Adverse Reaction

An AR is considered “unexpected” when its nature (specificity) or severity is not consistent with applicable product information as described in the safety information provided in the package inserts for Grazax® or not consistent with the known AR towards the different study procedures described in section 6.5.

6.7.1.4. Serious Adverse Event or Serious Adverse Reaction

A SAE or SAR is defined as any AE or AR that at any dose suggests a significant hazard, contraindication, side effect, or precaution. This includes, but is not limited to, any of the following events:

- Death: A death that occurs during the study or that comes to the attention of the investigator during the protocol-defined follow-up period must be reported whether it is considered treatment related or not.
- A life-threatening event: Any adverse experience that, in the view of the Investigator, places the participant at immediate risk of death.
- Inpatient hospitalization or prolongation of existing hospitalization.
- Persistent or significant disability or incapacity.
- An event that requires intervention to prevent permanent impairment or damage.
- An important medical event that may not result in death, be life threatening, or require hospitalization may be considered an SAE when, based on appropriate medical judgment, it may jeopardize the participant and may require medical or surgical intervention to prevent one of the outcomes listed above.
- Congenital anomaly or birth defect.

Medical judgement should be exercised in deciding whether an AE/AR is serious in other situations. Important AE/ARs that are not immediately life-threatening or do not result in death or hospitalisation but may jeopardise the subject or may require intervention to prevent one of the other outcomes listed in the definition above, should also be considered serious.

6.7.1.5. Suspected Serious Adverse Reaction (SSAR)

Any AR that is classed as serious *and* which is consistent with the information given about performed study procedures listed in section 6.5 and about Grazax® listed in the Summary of Product Characteristics (SmPC) or package inserts. Information on known AR of Grazax® can be further found at:

<http://emc.medicines.org.uk/>

6.7.1.6. Suspected Unexpected Serious Adverse Reaction (SUSAR)

Any SAR related to Grazax®/Grazax Placebo or a procedure performed in the study that is both unexpected and serious. Known side effects are listed in section 6.4 and 6.5. In case of occurrence of a SAR these sections will be checked. If the event is not listed as expected, or has occurred in a more serious form than anticipated, this will be considered a SUSAR.

6.7.2 Grading of adverse events/adverse reactions

The study site will grade the severity of AEs/ARs for the study medication according to the following criteria:

- All local reactions not associated with systemic signs or symptoms will be graded according to Table 6.
- All systemic reactions to AIT will be graded according to the WAO SCIT Reaction Grading System³⁵. The following modification will apply for AIT: Under Grade 1 (Symptoms/signs of 1 organ system present), “throat clearing (itchy throat)” is not considered a systemic reaction.

Table 6: Sublingual immunotherapy (local reactions) Grade Description²⁹

Symptom/sign (see Table I)	Grade 1: Mild	Grade 2: Moderate	Grade 3: Severe	Unknown severity
Pruritus/swelling of mouth, tongue, or lip; throat irritation, nausea, abdominal pain, vomiting, diarrhea, heartburn, or uvular edema	
 Not troublesome AND No symptomatic treatment required AND No discontinuation of SLIT because of local side effects 	
 Troublesome OR Requires symptomatic treatment AND No discontinuation of SLIT because of local side effects 	
 Grade 2 AND SLIT discontinued because of local side effects 	Treatment is discontinued, but there is no subjective, objective, or both description of severity from the patient/physician.

Each local AE can be early (<30 minutes) or delayed.

The study site will grade the severity of AEs/ARs for the following selected study procedures according to the following criteria:

- All local reactions to nasal biopsy will be recorded according to Table 7.
- All local reactions to allergen skin testing that are to be reported as AEs and are not associated with systemic signs or symptoms will be graded according to Table 8.
- Although very unlikely, systemic reactions related to either AIT tablet treatment, nasal challenge or intradermal or skin prick test procedures will be graded according to the WAO SCIT Systemic Reaction Grading System³⁵.

Table 7: Nasal biopsy procedure (local reactions)

Grade Description

1 Bleeding that does not respond to finger pressure, pain that does not respond to paracetamol, or symptoms which require a telephone consultation with a study physician.

2 Bleeding or pain that requires a visit to the doctor for treatment.

3 Bleeding or pain that requires hospitalization.

Table 8: Intradermal and skin prick test procedure (local reactions)

Grade Description

1 Bothersome (interfering with usual daily activities or sleep).

2 Bothersome (requiring medication).

3 Bothersome (requiring a visit to the study physician/emergency room for treatment).

The study site will grade the severity of AEs/ARs experienced by study participants not covered by Tables 5 through 7 or mentioned in the WAO criteria³⁵ according to the criteria set forth in the National Cancer Institute's *Common Terminology Criteria for Adverse Events, Version 4.0* (published May 28, 2009 and updated June 14, 2010). This document is found at this website:

http://evs.nci.nih.gov/ftp1/CTCAE/CTCAE_4.03_2010-06-14_QuickReference_5x7.pdf.

This document (referred to herein as the “NCI-CTCAE manual”) provides a common language to describe levels of severity, to analyse and interpret data, and to articulate the clinical significance of all AEs. AEs will be graded on a scale from 1 to 5 according to the following standards in the NCI-CTCAE manual:

- Grade 1 = mild adverse event.
- Grade 2 = moderate adverse event.
- Grade 3 = severe and undesirable adverse event.
- Grade 4 = life-threatening or disabling adverse event.
- Grade 5 = death.

For additional information and a printable version of the NCI-CTCAE manual, go to http://ctep.cancer.gov/protocolDevelopment/electronic_applications/ctc.htm#ctc_40

